3.1. Study Schematic

3.2. Discussion of Study Design

Paragraph 3

This is a Phase I, open-label, multiple-dose, multicenter, dose-escalation, first-time-in-human study conducted in two parts. In Part 1, an accelerated dose titration will be employed with one subject per dose level until the first instance of a \geq Grade 2 drug related non-hematological toxicity or dose limiting toxicity (DLT) (Section 3.3.3) occurs. Exceptions for except for pre-specified Grade 3 non-serious non-hematological drug related adverse events that would allow continuation of accelerated dose escalation are listed in Section 3.3.2.1. or dose limiting toxicity (DLT) (Section 3.3.3).

In the accelerated dose escalation cohorts and the 3+3 dose escalation cohorts, the dose will be escalated based on all available data, including PK data, and the safety profile information from prior cohorts, as well as the recommended predicted dose from Neuenschwander-B- a Continuous Reassessment Method (N-CRM) design analysis [Neuenschwander, 2008]. The N-CRM is a type of Bayesian adaptive dose-escalation scheme. The method is fully adaptive and makes use of all the DLT information available at the time of each dose assignment. The Fixed and Adaptive Clinical Trial Simulator (FACTS) will be used to conduct the N-CRM analysis. The DLT information on all subjects enrolled in the trial are used to update the estimated dose-toxicity relationship and to provide supportive information in addition to the 3+3 design in the next escalation/de-escalation decision.

After the accelerated dose titration, subjects will be enrolled in a standard 3+3 dose escalation design. Dose escalation will continue until an RP2D is determined or until an MTD or a dose of 3000 mg twice-weekly is reached [Maximum Feasible Dose (MFD)]. After the RP2D (or MTD/MFD) has been determined in Part1, then Part 2 expansion cohorts will be opened. In Part 2, subjects with will be assigned to one of two four cohorts based on disease and EZH2 mutation status.

Safety assessments will be performed weekly for the first 4 weeks and then at regular intervals as outlined in the Time and Events Table (Section 7.1).

Disease response in lymphoma and solid tumor subjects will be assessed everyas described in the T&E table (Section 7.1).

3.3.2 3+3 Dose Escalation Phase

Paragraph 3

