12.5.3. Treatment Comparisons

No formal hypothesis testing will be performed between dose cohorts. Safety, PK, PD marker, and efficacy summaries will be provided by dose cohort and planned time of assessment in Part 1 and by expansion cohort and planned time of assessment in Part 2.

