Hepatic Toxicity	
In first in human study EZH117208 (present study), an increase in level of ALT has been noted in the group of subjects receiving doses of 1800 mg to 3000 mg (single infusion dose). None of these ALT increases have been associated with increase in total bilirubin or INR and all have shown improvement following either withholding or discontinuing GSK2816126. The 3000 mg dose has been declared to exceed the MTD. The highest dose being explored in this study is 2400 mg.
 
In nonclinical species given GSK2816126, twice weekly for 2 and/or 4 weeks, changes in liver pathology (inflammation, hyperplasia) in dogs and clinical chemistry parameters (i.e. increases in ALT, AST, ALP, bilirubin and decreases in albumin) in rats and dogs were observed and were
	
Dosing at 3000 mg has been discontinued, with the highest dose being explored is at 2400 mg. Continued laboratory and clinical monitoring for liver dysfunction (LFT, coagulation parameters INR/PTT, other blood chemistry, clinical observation for jaundice). Dose management and stopping criteria as per guidelines for non-hematologic toxicity (Section 3.8.3 and Table 4) and hepatic safety monitoring (Section 8.3.1)

Potential Risk of Clinical Significance	Data/Rationale for Risk	Mitigation Strategy

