An evaluable subject in Table 2 is defined as a subject who has been on study for at least 28 days (one cycle). Evaluation of safety data from at least 1 subject during the accelerated dose titration or at least 3 subjects in the standard dose titration who have completed 28 days of dosing on study (one cycle) is required prior to defining a new dose and starting the next cohort. Once a higher dose has been cleared, subjects at lower dose levels who remain on study drug and have not experienced dose limiting toxicity will be allowed to escalate up to that level.

Reverting from 3+3 Dose Escalation to Accelerated Dose Titration: Once Grade 2 toxicity is seen in one subject, there are 2 scenarios where the accelerated dose escalation may be resumed.

- 1) If two additional subjects are added at the dose where Grade 2 toxicity was seen in the initial subject and if no Grade 2 or higher toxicity is seen in either of the 2 new subjects, the accelerated dose escalation may be resumed, or
- 2) If the 3+3 method is used and, at the next higher dose, the 3 subjects do not have a grade 2 or higher toxicity, the accelerated dose escalation may be resumed.
(Before any decision is made to reinitiate accelerated dose titration a discussion between the investigators and the GSK medical monitor is required)

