Part 1 PK/PD cohorts: Any dose level may be expanded up to 12 subjects in order to collect adequate data on safety, pharmacokinetics, or pharmacodynamics. Urine, bile, and additional blood samples may be collected following repeated administration for drug metabolite profiling and to obtain information on renal excretion of GSK2816126. Initially, optional pre- and post-treatment tumor biopsies will be requested. At MTD, mandatory collection of pre- and post-treatment tumor biopsies will be required for enrollment in a PK/PD cohort. Mandatory biopsies may be instituted at lower dose levels once evidence of target engagement has been demonstrated in surrogate tissue (e.g. H3K27me3 from PBMCs in blood); or if sufficient evidence of target engagement (e.g. dose dependence) is not observed in PD assay from surrogate tissue. Additional subjects may be enrolled at previously completed dose levels for the purpose of obtaining additional PK or PD data. A reduced PK schedule may be used in subjects enrolled to obtain additional PD data. These subjects may have the dose escalated to a higher completed dose level (not exceeding the MTD) once the necessary PK/PD procedures have been completed.

Section 3.3.5 Intra-subject Dose Escalation

Rationale for Change: Included additional text to clarify PK/PD and safety assessments for subjects who are approved for intra-subject dose escalation

REVISED TEXT

Decision on intra-subject dose escalation will be made after review of all safety data and approval by a GSK Medical Monitor and discussion with the investigator. In this case, the subject may begin dosing at the higher dose level as it will have already been demonstrated to be tolerable and monitoring will be performed as described in the protocol. Subjects approved for intra-subject dose escalation may require additional limited PK and/or PD sampling as determined by GSK Clinical Pharmacology. Additional safety assessments may be specified at the time of the dose escalation or schedule modification based on the safety profile in previous subjects at the higher dose level.

Section 3.3.7 Part 1: Futility and Efficacy Analysis for GCB-DLBCL Subjects

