All available data, including adverse events, changes in laboratory values and other safety parameters will be evaluated for each dose cohort in Part 1, in addition to futility and success analyses, and for each expansion cohort in Part 2.

Section 12.3.4 Interim Analysis

REVISED TEXT

12.3.4.1 Part 1

~~No formal interim analysis will be performed for Part 1 of the study. Safety, PK, and PD marker data will be examined during Part 1. Prior to determining the GSK2816126 dose for the next cohort, exploratory analyses will be conducted to assess the relationship of GSK2816126 dose levels with safety, PK and PD parameters using all data from available cohorts.~~

Futility and efficacy interim analysis of overall response rate will be performed continuously for GCB-DLBCL expansion cohort in Part 1 of the study, after 13 subjects have been enrolled. In addition, safety, PK, and PD marker data will be examined during Part 1. Prior to determining the GSK2816126 dose for the next cohort, exploratory analyses will be conducted to assess the relationship of GSK2816126 dose levels with safety, PK and PD parameters using all data from available cohorts. If success criteria are reached at an interim analysis for GCB-DLBCL at MTDRP2D twice-weekly every 3 out of 4 weeks followed by 1 week off, and the totality of data support opening Part 2, then Part 2 will begin and Part 1 expansion will close.

Full details of procedures and of the analyses planned at the interim analysis will be provided in the Reporting and Analysis Plan (RAP).

Section 12.3.4 Interim Analysis

REVISED TEXT

Section 12.3.4.2 Part 2

For each expansion cohort, after the initial ~~12-10~~ subjects have enrolled at the RP2D dose, response data will be reviewed on an ongoing basis and the number of responses observed will be compared with the stopping rules provided in Section ~~3.4~~12.2.2.. In

addition, safety, PK, and PD marker data will be analyzed. Full details of procedures and of the analyses planned at the interim analysis will be provided in the Reporting and Analysis Plan (RAP).

Section 12.4.1.4 Efficacy Analyses

REVISED TEXT

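### Part 1 safety is summarised by dose cohort although a subject's dose may change, so a summary by dose at onset should be added beside it

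*Protocol*

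**What the plan says.** Only the second part of the protocol file is at hand. It holds the amendment history, with Amendment 5 as the latest text.

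- **Unit of the safety summary.** Section 12.3.3.1 says "adverse events, changes in laboratory values and other safety parameters will be evaluated for each dose cohort in Part 1". The Statistical Methods paragraph of the synopsis likewise has descriptive safety analyses summarised and listed by cohort once the study ends. An earlier amendment's Section 12.5.3 used the same unit: "Safety, PK, PD marker, and efficacy summaries will be provided by dose cohort and planned time of assessment in Part 1".
- **Upward dose changes.** Section 3.3.2 provides that, once a higher dose is cleared, "subjects at lower dose levels who remain on study drug and have not experienced dose limiting toxicity will be allowed to escalate" to it. Section 3.3.5 adds that, after review and approval, "the subject may begin dosing at the higher dose level as it will have already been demonstrated to be tolerable".
- **Downward changes and return.** Section 3.9.1 reduces the dose by one level for toxicity. It allows later re-escalation with the Medical Monitor's approval once the toxicity has resolved.
- **A harm linked to dose received.** The hepatic toxicity row of Section 1.3.1 records that "an increase in level of ALT has been noted in the group of subjects receiving doses of 1800 mg to 3000 mg".
- **Other dose-safety work.** Under Section 12.3.4.1, before the next cohort's dose is set, "exploratory analyses will be conducted to assess the relationship of GSK2816126 dose levels with safety, PK and PD parameters". Section 2.1 has a Part 1 secondary objective relating exposure to safety.

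**The concern.** A table by cohort describes toxicity by dose only if subjects stay on the dose that defines their cohort. Here they need not. Suppose a subject enrolled at a low dose moves up to 1800 mg or more, and ALT then rises. If cohort means the enrolment dose, that event is counted at a dose the subject was no longer receiving. An event that starts after a reduction would, in the same way, stay with the higher cohort.

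The first kind of error raises the apparent rate at low doses and narrows the contrast with high doses. At stake is the descriptive picture of toxicity by dose level, which is part of the safety profile that informs the RP2D and of what will be known about tolerability at the lower levels. Very small cohorts make this worse. In the accelerated phase "an accelerated dose titration will be employed with one subject per dose level", so one event after escalation would read as 1 of 1 at a low dose.

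**Working it through.** The plan gives no figure on this point, so there is none to reproduce. The check has two steps.

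**Step 1: what cohort means.** Amendment 5 uses the word for an enrolment group.

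| Place | Use |
|---|---|
| Synopsis, Study Design | Subjects are enrolled into dosing cohorts |
| Section 3.3.2 | Safety data are reviewed before the next cohort starts; a subject already on study moves to a higher level |
| Section 3.3.5 | A subject moves to a higher dose level |
| Section 12.3.4.1 | A dose is chosen for the next cohort; exploratory work relates dose levels to safety |
| Section 12.3.3.1 | Safety is evaluated for each dose cohort |

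A move within a subject is described as a change of dose level and not as a change of cohort. The natural reading of Section 12.3.3.1 is therefore grouping by starting dose. No sentence in the text shown says so expressly, and none says the opposite.

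**Step 2: direction and possible size under that reading.** Let *l* be the ALT event risk while on a low dose, *h* the risk at 1800 mg or more, and *f* the share of low-dose starters later escalated to 1800 mg or more. The document gives none of these; all three are assumed. The two risks are taken as independent within a subject, and the high-dose cohort's own rate is taken as *h*.

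- Low-dose starters who stay have an event with probability *l*.
- Those who escalate have one with probability 1 − (1 − *l*)(1 − *h*).
- The rate shown for the low cohort is (1 − *f*)*l* + *f*[1 − (1 − *l*)(1 − *h*)] = 1 − (1 − *l*)(1 − *fh*).

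With *l* = 5%:

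| *h* | *f* | Low-cohort rate shown | Gap shown (*h* minus that rate) | Gap by dose at onset (*h* − *l*) |
|---|---|---|---|---|
| 20% | 0 | 5% | 15 points | 15 points |
| 20% | 25% | 1 − 0.95 × 0.95 = 9.75% | 10.25 points | 15 points |
| 20% | 50% | 1 − 0.95 × 0.90 = 14.5% | 5.5 points | 15 points |
| 40% | 0 | 5% | 35 points | 35 points |
| 40% | 25% | 1 − 0.95 × 0.90 = 14.5% | 25.5 points | 35 points |
| 40% | 50% | 1 − 0.95 × 0.80 = 24% | 16 points | 35 points |

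The direction is the same whenever *f* and *h* are above zero. With *f* = 0 there is no distortion.

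**The case against.** The strongest reply is that the defect is inferred. No passage assigns an event after escalation to the starting dose. Attribution by dose at onset is compatible with the wording and is an ordinary derivation rule for a Reporting and Analysis Plan. The safety-analysis section is not in the part of the protocol shown. The dose-safety relation is also examined elsewhere, through the exposure-safety objective and the exploratory analyses by dose level. Dose decisions rest on 28-day evaluable subjects, DLTs and all available data, not on an end-of-study table. The illustration rests wholly on assumed inputs.

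Most of this stands, and it rules out three stronger readings that a reader might draw:

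- **That ALT rises are in fact being reported under low doses.** The text does not say this.
- **That the known liver harm is hidden.** Section 1.3.1 describes the ALT increases by dose received and states that 3000 mg was declared to exceed the MTD, so the signal was seen.
- **That the MTD is misstated.** Under Section 3.3.2 a subject moves up only after the higher dose is cleared and without having had a DLT. The early observation at the assigned dose is therefore not mixed.

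The reply does not remove the point. Section 12.3.3.1 does fix a unit, and it is the cohort. In the text shown, the deferral to the Reporting and Analysis Plan in Section 12.3.4 concerns the interim analyses, and the one in Section 12.4.1.4 follows the efficacy text. The exploratory analyses serve the choice of the next dose. The exposure-safety objective does not change how adverse-event and laboratory tables are built.

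**Conclusion.** The point holds as a cheap improvement to the stated analysis, not as a demonstrated error. The protocol summarises Part 1 safety by dose cohort while letting a subject's dose change. On the natural reading of cohort, events that start after a change would sit under the starting cohort and dilute the descriptive dose-toxicity gradient.

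The size is unknown, because the protocol does not say how many subjects escalate. For ALT it is zero if no low-dose starter reaches 1800 mg or more. Under the assumed risks and with a quarter to a half escalated, the low-cohort rate would read 9.75% to 24% instead of 5%. Those figures illustrate a mechanism and do not estimate what happened in this trial. The conclusion rests on cohort meaning the enrolment dose. If the sponsor already intends attribution by dose at onset, one sentence saying so settles it.

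**What to change.** In Section 12.3.3.1, keep the by-cohort summary, with cycle-1 events at the assigned dose shown for the DLT assessment. Add a second summary of Part 1 adverse events and laboratory shifts by the dose last received before onset. Use as denominators the subjects and the infusions at risk at each dose, and flag subjects whose dose was escalated, reduced or re-escalated.

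This needs one derived variable, dose at onset, built from dosing and onset dates. It changes no dose and no clinical rule. The downside is that a subject can appear at more than one dose, so the columns do not sum to the number of subjects; a table footnote should say so.

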
www.crediblemeds.org (27 February 2015 9 January 2017)

Section 15.3 Appendix 3: Liver Chemistry Monitoring, Interruption Stopping and Follow-up Criteria

Rationale for Change: The Liver Events section was reorganized with updated tables and figures. Stopping/monitoring criteria for subjects with baseline ALT \leq 2.5xULN have not changed. Stopping/monitoring criteria rules were further clarified for subjects with documented liver metastases/tumor infiltration at baseline and entry criteria ALT $>$ 2.5xULN but $<$ 5xULN. Study treatment restart/rechallenge criteria was added. Details added to Appendix 3.

REVISED TEXT

Section 15.3.1 Liver Safety Stopping Criteria and Required Action and Follow up Assessments

Phase I/II liver chemistry stopping and increased monitoring criteria have been designed to assure subject safety and evaluate liver event etiology (in alignment with the FDA premarketing clinical liver safety guidance).

<http://www.fda.gov/downloads/Drugs/GuidanceComplianceRegulatoryInformation/Guidances/UCM174090.pdf>.

Phase I/II liver chemistry stopping criteria and required follow up assessments

Liver Chemistry Stopping Criteria – Liver Stopping Event Subject with entry criteria ALT≤ 2.5 x ULN	
ALT-absolute	ALT ≥ 5xULN
ALT Increase	ALT ≥ 3xULN persists for ≥4 weeks
Bilirubin^{1, 2}	ALT ≥ 3xULN and bilirubin ≥ 2xULN (>35% direct bilirubin)
INR²	ALT ≥ 3xULN and INR>1.5, if INR measured
Cannot Monitor	ALT ≥ 3xULN and cannot be monitored weekly for 4 weeks
Symptomatic³	ALT ≥ 3xULN associated with symptoms (new or worsening) believed to be related to liver injury or hypersensitivity
Liver Chemistry Stopping Criteria – Liver Stopping Event Including subjects with documented liver metastases/tumor infiltration at baseline AND entry criteria ALT>2.5 x ULN but ≤5 x ULN	
ALT-absolute	Both ALT ≥ 5xULN and ≥2x baseline value
ALT Increase	Both ALT ≥ 3xULN and ≥ 1.5x baseline value that persists for ≥4 weeks
Bilirubin^{1, 2}	ALT ≥ 3xULN and bilirubin ≥ 2xULN (>35% direct bilirubin)
INR²	ALT ≥ 3xULN and INR>1.5, if INR measured
Cannot Monitor	Both ALT ≥ 3xULN and ≥ 1.5x baseline value that cannot be monitored for 4 weeks
Symptomatic³	Both ALT ≥ 3xULN and ≥ 1.5x baseline value associated with symptoms (new or worsening) believed to be related to liver injury or hypersensitivity
Required Actions and Follow up Assessments following ANY Liver Stopping Event	
Actions	Follow Up Assessments

 Immediately discontinue study treatment Report the event to GSK within 24 hours Complete the liver event eCRF and complete an SAE data collection tool if the event also meets the criteria for an SAE² 	
 Viral hepatitis serology⁴ Blood sample for pharmacokinetic (PK) analysis, obtained approximately 48h after last dose⁵ Serum creatine phosphokinase (CPK) and lactate dehydrogenase (LDH)


 • Perform liver event follow up assessments • Monitor the subject until liver chemistries resolve, stabilize, or return to within baseline (see MONITORING below) • Do not restart/rechallenge subject with study treatment unless allowed per protocol and GSK Medical Governance approval is granted (refer to Appendix 3) • If restart/rechallenge is not granted, permanently discontinue study treatment and may continue subject in the study for any protocol specified follow up assessments 
MONITORING:
 
For bilirubin or INR criteria:
 
 • Repeat liver chemistries (include ALT, AST, alkaline phosphatase, bilirubin) and perform liver event follow up assessments within 24 hrs • Monitor subjects twice weekly until liver chemistries resolve, stabilize or return to within baseline • A specialist or hepatology consultation is recommended 
For All other criteria:
 
 • Repeat liver chemistries (include ALT, AST, alkaline phosphatase, bilirubin) and perform liver event follow up assessments within 24-72 hrs • Monitor subjects weekly until liver chemistries resolve, stabilize or return to within baseline 	
 • Fractionate bilirubin, if total bilirubin $\geq 2 \times \text{ULN}$ • Obtain complete blood count with differential to assess eosinophilia • Record the appearance or worsening of clinical symptoms of liver injury, or hypersensitivity, on the AE report form • Record use of concomitant medications on the concomitant medications report form including acetaminophen, herbal remedies, other over the counter medications • Record alcohol use on the liver event alcohol intake case report form 
For bilirubin or INR criteria:
 
 • Anti-nuclear antibody, anti-smooth muscle antibody, Type 1 anti-liver kidney microsomal antibodies, and quantitative total immunoglobulin G (IgG or gamma globulins). • Serum acetaminophen adduct high pressure liquid chromatography (HPLC) assay (quantifies potential acetaminophen contribution to liver injury in subjects with definite or likely acetaminophen use in the preceding week [James, 2009]). • Liver imaging (ultrasound, magnetic resonance, or computerised tomography) and /or liver biopsy to evaluate liver disease: complete Liver Imaging and/or Liver Biopsy eCRF forms.
--	--

1. Serum bilirubin fractionation should be performed if testing is available. If serum bilirubin fractionation is not immediately available, discontinue study treatment for that subject if ALT $\geq 3 \times \text{ULN}$ and bilirubin $\geq 2 \times \text{ULN}$. Additionally, if serum bilirubin fractionation testing is unavailable, record presence of detectable urinary bilirubin on dipstick, indicating direct bilirubin elevations and suggesting liver injury.
2. All events of ALT $\geq 3 \times \text{ULN}$ and bilirubin $\geq 2 \times \text{ULN}$ ($>35\%$ direct bilirubin) or ALT $\geq 3 \times \text{ULN}$ and INR >1.5 , if INR measured which may indicate severe liver injury (possible 'Hy's Law'), must be reported as an SAE (excluding studies of hepatic impairment or cirrhosis); INR measurement is not required and the threshold value stated will not apply to subjects receiving anticoagulants
3. New or worsening symptoms believed to be related to liver injury (such as fatigue, nausea, vomiting, right upper quadrant pain or tenderness, or jaundice) or believed to be related to hypersensitivity (such as fever, rash or

- eosinophilia)
4. Includes: Hepatitis A IgM antibody; Hepatitis B surface antigen and Hepatitis B Core Antibody (IgM); Hepatitis C RNA; Cytomegalovirus IgM antibody; Epstein-Barr viral capsid antigen IgM antibody (or if unavailable, obtain heterophile antibody or monospot testing); Hepatitis E IgM antibody
 5. Record the date/time of the PK blood sample draw and the date/time of the last dose of study treatment prior to blood sample draw on the eCRF. If the date or time of the last dose is unclear, provide the subject's best approximation. If the date/time of the last dose cannot be approximated OR a PK sample cannot be collected in the time period indicated above, do not obtain a PK sample. Instructions for sample handling and shipping are in the SRM.

Phase I/II Oncology liver chemistry increased monitoring criteria with continued therapy

Liver Chemistry Increased Monitoring Criteria – Liver Monitoring Event	
Criteria	Actions

Subject with entry criteria ALT≤2.5x ULN
 
ALT ≥3xULN but <5xULN and
 
bilirubin <2xULN, without symptoms believed to be related to liver injury or hypersensitivity and who can be monitored weekly for 4 weeks
 
Subject with documented liver metastases/tumor infiltration at baseline AND entry criteria ALT>2.5 x ULN but ≤5 x ULN
 
ALT ≥3x ULN and 1.5x baseline value but ALT <5x ULN and 2x baseline value and bilirubin <2xULN, without symptoms believed to be related to liver injury, or hypersensitivity and who can be monitored weekly for 4 weeks
	
 • Notify the GSK medical monitor within 24 hours of learning of the abnormality to discuss subject safety. • Subject can continue study treatment • Subject must return weekly for repeat liver chemistries (ALT, AST, alkaline phosphatase, bilirubin) until they resolve, stabilise or return to within baseline¹ • If at any time subject meets the liver chemistry stopping criteria, proceed as described above 
For subjects with entry criteria ALT≤2.5 x ULN
 
 • If, after 4 weeks of monitoring, ALT <3xULN and bilirubin <2xULN, monitor subjects twice monthly until liver chemistries normalize or return to within baseline. 
For subjects with documented liver metastases/tumor infiltration at baseline AND entry criteria ALT>2.5 x ULN but ≤5 x ULN
 
 • If, after 4 weeks of monitoring, ALT <3xULN and <1.5x baseline value, and bilirubin <2xULN, monitor subjects twice monthly until liver chemistries normalize or return to within baseline

1. For the purpose of these guidelines "baseline" refers to laboratory assessments performed closest and prior to first dose of study treatment

References

Section 15.3.2 Liver Safety – Study Treatment Restart or Rechallenge Guidelines

If subject meets liver chemistry stopping criteria do not restart/rechallenge subject with study treatment unless:

- GSK Medical Governance approval is granted (as described below),
- Ethics and/or IRB approval is obtained, if required, and
- Separate consent for treatment restart/rechallenge is signed by the subject

If GSK Medical Governance approval to restart/rechallenge subject with study treatment **is not granted**, then subject must permanently discontinue study treatment and may continue in the study for protocol-specified follow up assessments

1. Rechallenge Following Liver Stopping Events that are Possibly Related to Study Treatment

Following drug-induced liver injury, **drug rechallenge is associated with a 13% mortality across all drugs in prospective studies** [Andrade, 2009]. Clinical outcomes vary by drug, with nearly 50% fatality with halothane readministered within one month of initial injury. However, some drugs seldom result in recurrent liver injury or fatality.

Risk factors for a fatal drug rechallenge outcome include:

- hypersensitivity with initial liver injury (e.g. fever, rash, eosinophilia) [Andrade, 2009]
- jaundice or bilirubin >2xULN with initial liver injury (direct bilirubin >35% of total)
- subject currently exhibits severe liver injury defined by: ALT \geq 3xULN, bilirubin \geq 2xULN (direct bilirubin >35% of total), or INR \geq 1.5
- serious adverse event or fatality has earlier been observed with drug challenges [Papay, 2009]
- evidence of drug-related preclinical liability (e.g. reactive metabolites; mitochondrial impairment [Hunt, 2010])

Rechallenge refers to resuming study treatment following drug induced liver injury (DILI). Because of the risks associated with rechallenge after DILI this should only be considered for a subject for whom there is compelling evidence of benefit from a critical

or life-saving medicine, there is no alternative approved medicine available, and a benefit:risk assessment of rechallenge is considered to be favourable.

Approval by GSK for rechallenge with study treatment can be considered where:

- Investigator requests consideration of rechallenge with study treatment for a subject who is receiving compelling benefit with study treatment that exceeds risk, and no effective alternative therapy is available.
- Ethics Committee or Institutional Review Board approval for rechallenge with study treatment must be obtained, as required.
- If the rechallenge is approved by GSK Medical Governance in writing, the subject must be provided with a clear description of the possible benefits and risks of study treatment administration, including the possibility of recurrent, more severe liver injury or death.
- The subject must also provide signed informed consent specifically for the rechallenge with study treatment. Documentation of informed consent must be recorded in the study chart.
- Study treatment must be administered at the dose specified by GSK.
- Subjects approved by GSK Medical Governance for rechallenge with study treatment must return to the clinic twice a week for liver chemistry tests until stable liver chemistries have been demonstrated and then standard laboratory monitoring may resume as per protocol.
- If after study treatment rechallenge, subject meets protocol-defined liver chemistry stopping criteria, study treatment should be permanently discontinued.
- Medical Monitor, and the Ethics Committee or Institutional Review Board as required, must be informed of the subject's outcome following study treatment rechallenge.
- GSK to be notified of any adverse events, as per Section 8 of the protocol..

2. Restart Following Transient Resolving Liver Stopping Events NOT Related to Study Treatment

Restart refers to resuming study treatment following liver stopping events in which there is a clear underlying cause (other than DILI) of the liver event (e.g. biliary obstruction, pancreatic events, hypotension, acute viral hepatitis). Furthermore, there should be no evidence of alcoholic hepatitis or hypersensitivity, and the study treatment should not be associated with HLA markers of liver injury.

Approval by GSK for study treatment restart can be considered where:

- Investigator requests consideration for study treatment restart if liver chemistries have a clear underlying cause (e.g., biliary obstruction, hypotension and liver chemistries have improved to normal or are within 1.5 x baseline and ALT <3xULN).

- Restart risk factors (e.g. fever, rash, eosinophilia, or hypersensitivity, alcoholic hepatitis, possible study treatment-induced liver injury or study treatment has an HLA genetic marker associated with liver injury (e.g. lapatinib, abacavir, amoxicillin/clavulanate) are reviewed and excluded
- Ethics Committee or Institutional Review Board approval of study treatment restart must be obtained, as required.
- If restart of study treatment is approved by GSK Medical Governance in writing, the subject must be provided with a clear description of the possible benefits and risks of study treatment administration, including the possibility of recurrent, more severe liver injury or death.
- The subject must also provide signed informed consent specifically for the study treatment restart. Documentation of informed consent must be recorded in the study chart.
- Study treatment must be administered at the dose specified by GSK.
- Subjects approved by GSK Medical Governance for restarting study treatment must return to the clinic once a week for liver chemistry tests until stable liver chemistries have been demonstrated and then laboratory monitoring may resume as per protocol.
- If after study treatment re-start, subject meets protocol-defined liver chemistry stopping criteria, follow usual stopping criteria instructions.
- Medical Monitor, and the Ethics Committee or Institutional Review Board as required, must be informed of the subject's outcome following study treatment restart.
- GSK, or designee, to be notified of any adverse events, as per Section 8.

References:

Hunt, CM. Mitochondrial and immunoallergic injury increase risk of positive drug rechallenge after drug-induced liver injury: A systematic review. *Hepatol.* 2010;52:2216-2222.

Section 15.4 Appendix 4 Response Criteria

Rationale for Change: included missing criteria for confirmation scans for assigned PR and CR.

REVISED TEXT**Complete Response**

To be assigned a status of complete response, all changes must be confirmed by repeat assessments performed no less than four weeks after the criteria for CR were met.

1. Complete disappearance of all detectable clinical evidence of disease and disease related B-symptoms, if present prior to therapy.

Partial Response

To be assigned a status of complete response, all changes must be confirmed by repeat assessments performed no less than four weeks after the criteria for PR were met.

1. At least a 50% decrease from baseline in the SPD of up to six of the largest dominant nodes or nodal masses.
2. No increase in the size of the liver or the spleen. No unequivocal progression in any nonmeasurable or nondominant site.
3. Splenic and hepatic nodules must regress by $\geq 50\%$ in SPD compared to baseline. If only a single nodule/lesion, it must regress by $\geq 50\%$ in the greatest transverse diameter compared to baseline.
4. With the exception of splenic and hepatic nodules, involvement of other organs is accessible and no measurable disease should be present.
5. Bone marrow assessment is not relevant for determination of a PR if the sample was positive prior to treatment. However, if positive, the cell type should be specified. Subjects who ~~are~~ achieve CR criteria above, except for persistent morphologic bone marrow involvement will be considered partial responders. When the bone marrow was involved before therapy and a clinical CR was achieved, but no bone marrow assessment after therapy, subjects must be considered partial responders.

Relapsed Disease (after CR)/Progressive Disease (after PR, SD)

Criteria for determining PD for new lesions and target lesions are shown in Table 19Table 16

Table 4619 Criteria for determining PD for new lesions and target lesions

Section 15.5 Appendix 5: RECIST 1.1

Rationale for Change: Clarified that baseline bone scans are to be taken as clinically indicated.

REVISED TEXT

I. Efficacy Assessment

- The following are required at baseline: CT for Chest/Abdomen/Pelvis or MRI for Abdomen/Pelvis and clinical disease assessment for palpable lesions, brain scan and bone scan (bone scan as clinically indicated). At each post baseline assessment, evaluations of the sites of disease identified by these scans are required except for brain scan and bone scans. Brain and Bone scans should be performed as clinically indicated.

A baseline bone scan should be performed as clinically indicated is required for all subjects. For subjects without bone disease at baseline, subsequent bone scans should only be performed as clinically indicated (e.g. presentation of bone pain). For subjects with bone disease at baseline, a bone scan is required as clinically indicated. In addition, in order to assign a response of CR in a subject with bone disease at baseline, a bone scan must be performed 1 week prior to 4 weeks after.

Section 15.5 Appendix 5: RECIST 1.1

REVISED TEXT

IIIg. Independent Review

Disease progression and response evaluations may will be collected centrally during the study and may be reviewed or analyzed by an independent central reviewer. Details will be provided in the SPM.

